8.7. Biometric Report

The biometric report lies within the responsibility of the biostatistician of the clinical trial. The sponsor has to make every effort to acquire a complete data set for statistical analysis. The trial report has to be completed within a reasonable time.

9. Safety

9.1. Definition of Adverse Events and Side Effects

9.1.1. Adverse Events

Any untoward clinical relevant medical occurrence in a volunteer or clinical investigation subject to whom a pharmaceutical product had been administered and which does not necessarily have a causal relationship with this treatment. An AE can therefore be any clinical relevant unfavorable and unintended sign (including an abnormal laboratory finding), clinical relevant symptom, or disease temporally associated with the use of a medicinal (investigational) product, whether or not related to the medicinal (investigational) product.

An AE may be:

- New clinical relevant symptoms/ medical conditions
- New clinical relevant diagnosis
- Clinical relevant changes of laboratory parameters
- Diseases and medical consequences of an accident
- Worsening of medical conditions/ diseases existing before clinical trial start
- Recurrence of disease
- Clinical relevant increase of frequency or intensity of episodical diseases

A pre-existing disease or symptom will not be considered an AE unless there will be an untoward change in its intensity, frequency or quality. This change will be documented by the investigator.

In general, abnormal laboratory findings or clinical events without clinical significance (based on the investigator's judgement) should not be recorded as AEs.

Surgical procedures themselves are not AEs; they are therapeutic measures for conditions that require surgery. The condition for which the surgery is required may be an AE. Planned surgical measures permitted by the clinical trial protocol and the condition(s) leading to these measures are not AEs, if the condition leading to the measure was present prior to inclusion into the trial.

AEs are classified as "non-serious" or "serious".

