The main (per definition) adverse event identified for CoVac-1 is the induction of a granuloma locally at injection site (max. grade 2 in 33% of subjects). These totally asymptomatic granulomas were still detectable on day 28 (time of interim safety analysis). However, it should be noted that granuloma development represents an expected and, even more, intended local reaction after vaccination that is required to enable the continuous local priming of SARS-CoV-2 specific T cells and thus the induction of long-lasting T cell responses while at the same time preventing systemic inflammation. Granuloma formation was also rarely reported after mRNA-based vaccines⁹⁷, where it required systemic steroid treatment. CoVac-1 induced granulomas, in contrast, did not require any investigator-initiated medication and did not affect the daily life activities, in particular the working ability, of our study subjects.

Protocol		
Protocol code and Short Title:	P-pVAC-SARS-CoV-2	Date/Version:08.03.2021/V1.4

Conclusion

Together, in our view the available safety and immunogenicity data of CoVac-1 provide a profound rationale for the continued evaluation of CoVac-1 and thus conduct of the second part of the study. This is based, among others, on the comparison to the three vaccine candidates already approved by the EMA, which showed a clear superiority of CoVac-1 to induce SARS-CoV-2 specific T cell immunity, in terms of frequency, intensity and diversity of T cell responses. Thus, especially in the light of emerging mutations and concerns regarding long-term humoral immunity, CoVac-1 represents a highly promising vaccine candidate to combat COVID-19.

The interim safety and immunogenicity data were presented to the DSMB and all DSMB members agreed with and support the conduct of the second study part.

1.4. Data and Safety Monitoring Board (DSMB):

An independent Data and Safety Monitoring Board (DSMB) will be assembled. The DSMB will be composed of independent experts in the field of immunology and infectiology assessing the progress, safety data and critical efficacy endpoints. The mission of the DSMB is to ensure the ethical conduct of the trial and to protect the safety interests of participants in this trial.

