The investigator will review all information obtained from the screening procedures via an eligibility form. The investigator will confirm, in writing, whether the subject fulfils all criteria for eligibility. Volunteers who fulfil all the inclusion criteria and none of the exclusion criteria will be eligible to participate in the trial. Screening failures, i.e. screened volunteers not in compliance with all criteria, are to be excluded and the reason will be recorded in the volunteer records. Information of volunteer's trial participation can be provided to the volunteer's general practitioner if the volunteer agrees.

6.1.3. *Enrolment*

A volunteer is considered for screening when he or she has signed the Informed Consent form.

In case of confirmation of volunteer's eligibility (volunteers must meet all inclusion criteria and must not meet any exclusion criteria), volunteer will be registered under a specific Vol. ID on a subjects log kept at the trial site. Only these volunteers are enrolled in the study, all others are assessed as screening failures.

The study is open-label.

6.1.4. *Randomisation*

No randomisation will be done in this clinical trial.

6.1.5. *Concomitant Medication and Treatments*

Relevant additional medications and treatments administered to the subjects on entry to the trial or at any time during the trial are regarded as concomitant medications and treatments and must be documented on the appropriate pages of the CRF.

6.1.6. *Permitted Prior and Concomitant Medications and Treatments*

The following concomitant medications and treatments are permitted during the trial.

Part I: No concomitant medication, apart from contraception for FCBP.

Part II : Any concomitant medication (already applied at screening) for e.g. other diseases are allowed except for medications stated in section 6.1.7.

6.1.7. *Prohibited Prior and Concomitant Medications and Treatments*

The following concomitant medications and treatments are prohibited during the trial:

Protocol		
Protocol code and Short Title:	P-pVAC-SARS-CoV-2	Date/Version:08.03.2021/V1.4

- Immunosuppressive agents apart from (≤ 10 mg prednisolone or equivalent)
- During the trial, other vaccinations or non-urgent medical interventions are prohibited. Initiation of new medications, regardless of indication must be discussed with the investigator and must be noted on the participant's record.

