- Medical history, anamnestic evaluation of SARS-CoV-2 specific symptoms
- T-cell response, approximately 60 ml blood
- Serological response, approximately 15 ml blood

6.2.7. *Volunteer's diary/card*

Each patient included in the P-pVac-SARS-CoV-2 study will receive a volunteer's card, which states that he/she is participating in the study (Appendix 13.4). This will also include a 24h emergency contact number. Furthermore, each patient will be provided with a volunteer's diary to note their symptoms daily (Appendix 13.3)

6.2.8. *Unscheduled Visit*

Subjects may contact the investigator at any time for an unscheduled phone or on-site visit should they experience clinical symptoms or signs following injection. At all unscheduled visits, the following minimum assessment will be performed: Questions concerning the history of the present illness as well as the subject's general health and lifestyle. Findings resulting in (S)AEs

Protocol		
Protocol code and Short Title:	P-pVAC-SARS-CoV-2	Date/Version:08.03.2021/V1.4

will be documented and reported as indicated. All other symptoms/signs will be reported on the next scheduled visit on eCRF.

Upon occurrence of symptoms characteristic of SARS-CoV-2 (i. e. cough, fever (cut-off $>39^{\circ}\text{C}$), loss of taste and smell, limb pain) at any time until day 56, subjects are supposed to get in touch with the investigator. Investigator will initiate SARS-CoV-2 testing for the volunteer (nose or mouth swab followed by PCR per institutional guidelines). If the test is positive, patients should be treated per investigators discretion. Positive results must be recorded as an AESI (section 9.1.4). Negative results will be followed by a second testing $\geq 24\text{h}$ later. Only upon the second negative test, patients are considered negative, all others must be reported as positive.

If participants are positively tested for SARS-CoV-2, all accompanying symptoms and treatments (e.g. hospitalisation, ICU) are recorded

Medically attended AEs and all SAEs will be recorded, and concomitant medication or vaccination will be noted. After identifying the history of the present illness and performing corresponding exams or laboratory tests, the investigator will decide on the best course of treatment according to standard medical practice.

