9.3.2. Assessment of Severity and Causality

The investigator will also provide an assessment of the severity of the event according to CTCAE criteria (Version 5.0) and causal relationship between the event and each of the investigational products or trial procedures.

AEs and SAEs should be evaluated for severity according to the following scale:

- Grade 1 Mild; asymptomatic or mild symptoms; clinical or diagnostic observations only; intervention not indicated.
- Grade 2 Moderate; minimal, local or noninvasive intervention indicated; limiting age-appropriate instrumental Activities of Daily Living (ADL).
- Grade 3 Severe or medically significant but not immediately life-threatening; hospitalization or prolongation of hospitalization indicated; disabling; limiting self care ADL.
- Grade 4 Life-threatening consequences; urgent intervention indicated.
- Grade 5 Death related to AE.

The investigator must determine the causal relationship between the administration of IMP and the occurrence of an AE/SAE as defined below:

Related: There is a reasonable possibility that the SAE may be related to the IMP (e.g. favorable temporal relationship, positive dechallenge: symptoms are receding when IMP is withdrawn or the dose reduced, positive rechallenge: symptoms are reappearing when the IMP is reintroduced or the full dose is re-administered)

Not Related: There is no reasonable possibility that the SAE is related to the IMP (e.g. there is a plausible alternative cause for the SAE that better explains the occurrence of the SAE)

Outcome of AEs

The outcome of an AE at the time of the last observation will be classified as:

Recovered/ resolved	All signs and symptoms of an AE disappeared without any sequels at the time of the last interrogation.
Recovering/ resolving	The intensity of signs and symptoms has been diminishing and/ or their clinical pattern has been changing up to the time of the last interrogation in a way typical for its resolution.
Not recovered/ not resolved	Signs and symptoms of an AE are mostly unchanged at the time of the last interrogation.

Protocol		
Protocol code and Short Title:	P-pVAC-SARS-CoV-2	Date/Version:08.03.2021/V1.4

Recovered/ resolved with sequel	Actual signs and symptoms of an AE disappeared but there are sequels related to the AE.
Fatal	Resulting in death. If there are more than one AE, only the AE leading to death (possibly related) will be characterized as 'fatal'.

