Unknown	The outcome is unknown or implausible and the information cannot be supplemented or verified.

9.3.3. *Action taken*

No action will be taken with regards to the IMP as the vaccine is applied only once.

9.3.4. *Sponsors Assessment of the SAEs*

All SAE will be subject to a second assessment by the trial Sponsor or authorized second assessors, e.g. CI.

The second assessor will fill out a 'Second Assessment Form' for each SAE containing.

- Event serious yes/no
- Relationship between SAE and IMP/study procedure
- Expectedness of SAE according to the reference document: IB CoVac-1 peptide vaccine V1.0 dated 22.5.2020.
- Benefit / risk assessment for the trial regarding change as a result of SAE.

9.3.5. *Follow-up of Initial Report*

Information not available at the time of the initial report (e.g. end date for the AE or laboratory values received after the report) must be documented on a "Serious Adverse Event" form with the box "Follow-up" checked under "Report type".

All volunteers who have AEs, whether considered associated with the use of the investigational products or not, must be monitored to determine the outcome as far as possible. The clinical course of the AE will be followed up according to accepted standards of medical practice even after the end of the period of observation, until a satisfactory explanation is found or the investigator considers it medically justifiable to terminate follow-up. Should the AE result in death, a full pathologist's report should be supplied, if possible.

The sponsor will identify missing information for each SAE report and will require follow up information in regular intervals from the investigators until all queries are resolved or no further information can be reasonably expected. All responses to queries and supply of additional

information by the investigator should follow the same reporting route and timelines as the initial report.

9.3.6. *Exception of reporting*

As this is a prophylactic vaccination trial with application of CoVac-1 in healthy adults, no exception of reporting for AEs are made.

9.3.7. *Suspected Unexpected Serious Adverse Reaction (SUSAR)*

SAEs that are both suspected, i.e. possibly related to IMP, and ‘unexpected’, i.e. the nature and/ or severity of which is not consistent with the applicable product information are to be classified as Suspected Unexpected Serious Adverse Reactions (SUSARs).

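### Section 9.1.1 tells investigators not to record clinical events they judge insignificant, so low-grade unsolicited events can drop out of a primary endpoint that counts AEs of every grade

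*Supplement*

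**What the plan says.** The AE definition in section 9.1.1 of V1.4 opens with "Any untoward clinical relevant medical occurrence in a volunteer or clinical investigation subject to whom a pharmaceutical product had been administered". The same qualifier is repeated for signs and symptoms, and in the list of examples for new symptoms or conditions, new diagnoses, laboratory changes and more frequent or intense episodic disease. The section then adds: "In general, abnormal laboratory findings or clinical events without clinical significance (based on the investigator's judgement) should not be recorded as AEs". No criterion for relevance or significance is given.

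Other sections bear on the same events:

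- **2.1.1:** the primary endpoint is the nature, frequency and severity of AEs and/or SAEs associated with the vaccine. Unsolicited AEs count to day 56. No minimum grade is set.
- **8.3:** toxicity and safety are reported as absolute and relative frequencies by CTCAE grade.
- **9.3.2:** the lowest grade is "Grade 1 Mild; asymptomatic or mild symptoms; clinical or diagnostic observations only; intervention not indicated".
- **9.3.6:** because this is a prophylactic vaccine in healthy adults, "no exception of reporting for AEs are made".
- **6.4.2:** Grade 1-2 laboratory abnormalities become AEs only under two stated criteria (accompanying symptoms, or a change in concomitant therapy). Clinical events have no comparable criteria.
- **6.1.3:** "The study is open-label". There is one arm.

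**The concern.** For a first-in-human vaccine, the table of mild and moderate events by grade is a main product of the trial. Section 9.1.1 places a judgement ahead of that table: an event set aside as insignificant never becomes an AE, so it is neither graded nor counted. The events most exposed are those that the severity scale puts in Grade 1, namely asymptomatic findings and observations that need no intervention.

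The rule acts in one direction, since it can remove events but cannot add them. With no control arm, nothing in the data would show how much had been removed. Two investigators could follow the protocol correctly and report different Grade 1 frequencies.

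**Working it through.** **1. The plan's own figures.** Section 8.1.1 gives n = 33 evaluable, P0 = 0.0001, P1 = 0.05 and rejection at one or more vaccine-associated SAEs.

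- Power = 1 - (1 - 0.05)^33 = 0.816, as stated.
- Actual alpha = 1 - (1 - 0.0001)^33 = 0.0033, stated as 0.003.
- Enrolment = 33 / (1 - 0.075) = 35.7, rounded up to 36, as stated.

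These figures rest on SAEs, which a relevance filter would not plausibly remove. The AE-based holding rules in 6.5 start at Grade 3. So no decision rule and no design figure changes.

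**2. Path of a mild unsolicited symptom, taking the text literally.**

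- The volunteer reports it in the diary, at a visit or at an unscheduled contact.
- 9.1.1 asks whether it is clinically relevant. If the investigator thinks not, the instruction is not to record it as an AE.
- 9.3.1 requires all AEs to be documented, Table 1 footnote 11 requires a grade for each AE, and 9.3.6 allows no reporting exception. All three apply only to what has already passed 9.1.1, so none of them brings the event back.
- 8.3 then tabulates AEs by grade without it.

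**3. What is protected and what is not.**

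| Type of event | Position under V1.4 |
|---|---|
| Solicited local and systemic reactions | Predetermined list in 9.1.2, diary support for 28 days (2.1.1) |
| Granuloma | Listed as a solicited ADR (9.1.2) and as an AESI (9.1.4) |
| Grade 1-2 laboratory values | Objective criteria in 6.4.2 |
| SAEs | Separate definition in 9.1.5 and separate reporting form |
| Low-grade unsolicited symptoms and examination findings, to day 56 | Investigator's judgement only |

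Only the last row is exposed.

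**4. Size.** The documents give neither the rate of mild unsolicited events nor the share that would be judged insignificant. The following is therefore an assumption, shown only to indicate how the rule acts. If an event has true rate p and a share s is recorded, the chance that none is recorded among 36 volunteers is (1 - p·s)^36.

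| Assumed p | s = 1 | s = 0.75 | s = 0.5 | s = 0.25 |
|---|---|---|---|---|
| 10% | 2.3% | 6.0% | 15.8% | 40.2% |
| 5% | 15.8% | 25.3% | 40.2% | 63.6% |

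Nothing in the documents indicates which column applies.

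**The case against.** The strongest reply is that the protocol captures mild complaints in several other places.

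- The diary (Appendix 14.3) asks every day to d27 about other complaints, not only solicited ones.
- Table 1 collects vaccine-related and unrelated signs and symptoms at V1 to V5.
- Section 6.2.8, besides stating "Medically attended AEs and all SAEs will be recorded", sends all other symptoms and signs to the eCRF at the next scheduled visit.

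This stands as far as collection goes. A reader who took 6.2.8 to cover medically attended events alone would be misreading it. But these entries are not classed or graded as AEs, and the endpoint counts AEs.

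A second reply is that relevance and severity are different axes: a mild event can be clinically relevant, and 9.3.2 grades only what already qualifies. That makes the sections formally compatible, so this is a poor fit rather than a flat contradiction. It does not help an investigator who faces an asymptomatic observation that needs no intervention, which is both a textbook Grade 1 finding and a natural candidate for being called insignificant.

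Third, Part I recorded mild events freely under the same 9.1.1 wording. Itching (83%) and skin ulceration (8%) were reported (5.7.2.1) although neither was then on the solicited list. This is reassuring about practice, but reported events cannot show what was left out.

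Three stronger readings should be set aside:

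- **Granuloma.** A reader might infer from section 1.3 ("These totally asymptomatic granulomas were still detectable on day 28") that granulomas could be omitted. They are a named solicited ADR and AESI, and all Part I volunteers had one recorded.
- **Comparison by part.** A reader might infer that the subgroup analysis in 8.4 is distorted. This is a single-centre trial, and nothing shows that judgement differs between Parts I and II.
- **Open-label bias.** With one arm there can be no differential recording between arms. The open label means only that the judgement is made by staff who know that every volunteer was vaccinated.

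**Conclusion.** The point holds in a limited form. As written, 9.1.1 can cause under-counting of low-grade unsolicited clinical events and examination findings between injection and day 56, in a primary endpoint that sets no lower grade limit. The direction is certain if the rule is followed. The amount cannot be estimated from the documents, and they contain no evidence that events have in fact been lost.

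The conclusion assumes that investigators apply the exclusion sentence literally and that the AE tables are built from AE records, not from the separate signs-and-symptoms entries. The effect is confined to descriptive frequencies. The wording should be changed, but it does not put the confirmatory safety rule in doubt.

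**What to change.** - **9.1.1, definition and list:** delete *clinical relevant* where it qualifies occurrences, signs, symptoms, conditions, diagnoses and episodic disease.
- **9.1.1, exclusion sentence ("abnormal laboratory findings or clinical events without clinical significance"):** delete *or clinical events*, so that it covers laboratory findings only.
- **9.1.1, new sentence:** every untoward sign or symptom in the AE collection period is recorded and graded, including Grade 1. The investigator's view of clinical significance is captured as an attribute of the record and is not a condition of entry.
- **6.4.2:** leave the laboratory rule as it is.
- **6.2.8 (optional, for consistency):** say that all AEs are recorded at unscheduled visits.

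The cost is a change of wording in one or two sections and a few more Grade 1 entries per volunteer. Sample size, visits and stopping rule stay the same.

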9.1.2. Adverse Drug Reaction

An Adverse Drug Reaction (adverse reaction: undesirable effect) is a response to a medicinal product which is noxious and unintended. Adverse reactions may arise from use of the product within or outside terms of the marketing authorisation or from occupational exposure. Use

Protocol		
Protocol code and Short Title:	P-pVAC-SARS-CoV-2	Date/Version:08.03.2021/V1.4

outside the marketing authorisation includes off-label use, overdose, misuse, abuse and medication errors.

An unexpected Adverse Drug Reaction (ADR) is a reaction which nature or severity is not consistent with the applicable product information available for the IMP.

Expected ADRs are listed in the appropriate reference documents, e.g. Investigator's Brochures; and below:

A solicited AE/ADR is a predetermined event, which may reflect safety concerns related to the investigational product and is, at least for the local solicited AEs, expected. The solicited ADR/AEs (local and systemic) for this study include:

Local solicited ADRs:

- Swelling at site of injection
- Erythema at site of injection
- Pain or itching at site of injection
- Formation of granuloma at the injection site
- Superficial skin ulceration

Systemic solicited AEs:

- Fever
- Chills
- Myalgia (described to the subject as generalized muscle aches)
- Arthralgia (described to the subject as generalized joint aches)
- Fatigue
- Headache
- Gastrointestinal symptoms (loss of appetite, nausea, vomiting, abdominal pain, and/or diarrhoea)

A grading for severity of ADRs can be found in appendix 14.5 as guidance.

9.1.3. ***Expectedness***

An 'unexpected' adverse event is one the nature or severity of which is not consistent with the applicable product information, e.g. Investigator's Brochure (IB). Furthermore, reports which

add significant information on specificity or severity of a known adverse reaction are counted as 'unexpected' events.

